3.4 Prednisone (NSC-10023)

a. DESCRIPTION

Prednisone is a glucocorticoid rapidly absorbed from the GI tract.

b. TOXICOLOGY

Human Toxicology: Possible adverse effects associated with the use of prednisone are: fluid and electrolyte disturbances, congestive heart failure in susceptible persons, hypertension, euphoria, personality changes, insomnia, mood swings, depression, exacerbation of infection (e.g., tuberculosis), exacerbation or symptoms of diabetes, psychosis, muscle weakness, osteoporosis, vertebral compression fractures, pancreatitis, esophagitis, peptic ulcer, dermatologic disturbances, convulsions, vertigo and headache, endocrine abnormalities, ophthalmic changes, and metabolic changes. Some patients have experienced itching and other allergic, anaphylactic or other hypersensitivity reactions. Withdrawal from prolonged therapy may result in symptoms including fever, myalgia and arthralgia. Phenytoin phenobarbital and ephedrine enhance metabolic clearance of corticosteroids.

Corticosteroids should be used cautiously in patients with hypothyroidism, cirrhosis, ocular herpes simplex, existing emotional instability or psychotic tendencies, nonspecific ulcerative colitis, diverticulitis, fresh intestinal anastomoses, peptic ulcer, renal insufficiency, hypertension, osteoporosis and myasthenia gravis. Immunization procedures (especially smallpox vaccination) should not be undertaken in patients on corticosteroids.

c. PHARMACOLOGY

Kinetics: Natural and synthetic glucocorticoids are readily and completely absorbed from the GI tract. Prednisone is very slightly soluble in water. Glucocorticoids have salt-retaining properties. The anti-inflammatory property of this drug is its ability to modify the body's immune system. On the other hand, glucocorticoids suppress the body's response to viral as well as bacterial infections. Equivalent doses are as follows:

Dexamethasone	Methyl-prednisolone and Triamcinolone	Prednisolone and Prednisone	Hydrocortisone	Cortisone
0.75 mg	4 mg	5 mg	20 mg	25 mg

Formulation: Prednisone is available in 2.5 mg, 5 mg, 10 mg, 20 mg and 50 mg tablets.

Storage and Stability: Prednisone should be stored at room temperature.

Administration: Prednisone is administered orally.

Supplier: Prednisone is commercially available and should be purchased by third party. Prednisone will not be supplied by the NCI.

4.0 **STAGING CRITERIA**

(TAKEN FROM THE MANUAL FOR STAGING OF CANCER, AJCC, FIFTH EDITION.)

DEFINITION OF TNM

Clinical Staging. Primary tumor assessment includes digital rectal examination of the prostate and histologic or cytologic confirmation of prostatic carcinoma.

Pathologic Staging. Histologic examination of the resected specimen is required. Total prostatectomy and pelvic lymph node dissection are required for pathologic staging.

Definition of TNM

Primary Tumor, Clinical (T)

- | | |
|-------|--|
| TX | Primary tumor cannot be assessed. |
| T0 | No evidence of primary tumor. |
| T1 | Clinically inapparent tumor not palpable or visible by imaging |
| T1a | Tumor incidental histologic finding in 5% or less of tissue resected |
| T1b | Tumor incidental histologic finding in more than 5% of tissue resected |
| T1c | Tumor identified by needle biopsy (e.g., because of elevated PSA) |
| <hr/> | |
| T2 | Tumor confined within the prostate* |
| T2a | Tumor involves one lobe |
| T2b | Tumor involves both lobes |
| <hr/> | |
| T3 | Tumor extends through the prostatic capsule** |
| T3a | Extracapsular extension (unilateral or bilateral) |
| T3b | Tumor invades the seminal vesicle(s) |
| <hr/> | |
| T4 | Tumor is fixed or invades adjacent structures other than the seminal vesicles: bladder neck, external sphincter, or rectum, levator muscles and/or pelvic wall |

*Note: Tumor found in one or both lobes by needle biopsy, but not palpable or reliably visible by imaging, is classified as T1c.

**Note: Invasion into the prostatic apex or into (but not beyond) the prostatic capsule is not classified as T3, but as T2.

Primary Tumor, Pathologic (pT)

- | | |
|--------|----------------|
| pT2*** | Organ confined |
| pT2a | Unilateral |
| pT2b | Bilateral |

-
- pT3 Extraprostatic extension
 pT3a Extraprostatic extension
 pT3b Seminal vesicle invasion
-

pT4 Invasion of bladder, rectum

***Note: There is no pathologic T1 classification.

Regional Lymph Nodes (N)

- NX Regional lymph nodes cannot be assessed
N0 No regional lymph node metastasis
N1 Metastasis in a single lymph node or nodes.

Distant Metastasis* (M)**

- MX Distant metastasis cannot be assessed
M0 No distant metastasis
M1 Distant metastasis
 M1a Nonregional lymph node(s)
 M1b Bone(s)
 M1c Other site(s)

***NOTE: When more than one site of metastasis is present, the most advanced category is used. pM1c is most advanced.

Revised 4/15/00

Amended 7/1/00

S9921

Revised 5/15/00

Revised 1/1/01

Page 14

Revised 6/1/00

Revised 7/1/01

Revised 4/1/02

Amended 2/14/06

5.0 ELIGIBILITY CRITERIA

Each of the criteria in the following section must be met in order for a patient to be considered eligible for registration. Use the spaces provided to confirm a patient's eligibility. For each criterion requiring test results and dates, please record this information on the Prestudy Form and submit to the Data Operations Center in Seattle (see Section 14.0). Any potential eligibility issues should be addressed to the Data Operations Center in Seattle at [name] prior to registration.

SWOG Patient No. _____

Patient's Initials (L, F, M) _____

- ____ 5.1 All patients must have a histologic diagnosis of adenocarcinoma of the prostate and must be considered to have **clinically localized disease (Stage T1-T3, N0, M0)**, and be considered operable for cure by their primary urologic surgeon.

Patients must have had a radical prostatectomy within 120 days prior to registration **and must fulfill one or more** of the following criteria (from pathologic analysis of the radical prostatectomy specimen) **check all that apply:**

- ____ a. Pathologic Gleason's sum of equal or greater than 8.
- ____ b. pT3b (seminal vesicle) or pT4 or N1.
- ____ c. Pathologic Gleason's sum of 7 and positive margin.
- ____ d. Patients who have either a preoperative serum PSA value of > 15 ng/ml, or a biopsy Gleason score > 7, or a serum PSA level of > 10 ng/ml and a biopsy Gleason score > 6 are eligible.

- ____ 5.2 Serum testosterone must be obtained within 28 days prior to registration.
- ____ 5.3 Patients must have a performance status of 0 - 1 by Southwest Oncology Group criteria (see Section 10.3).
- ____ 5.4 Prior neoadjuvant hormonal therapy (of ≤ 4 months duration) prior to radical prostatectomy is allowed provided that the patient has fulfilled the clinical eligibility criteria prior to hormonal treatment. Patients may have started hormonal therapy post-prostatectomy but prior to registration to this study (see Sections 5.2 and 5.5 for other requirements).

No other therapy aimed at the treatment of this diagnosis may have been given or may be planned while the patient is receiving protocol treatment. The use of low dose megace (< 40 mg/day) for the treatment of hot flashes is allowed.

Patients must not have received prior radiation therapy. If the treating physician wishes to have RT administered, then the patient should be registered to the study FIRST and then optional RT can be given on protocol. All RT should be documented on the **S9921** Treatment Form (Form #38859).

SWOG Patient No. _____

Patient's Initials (L, F, M) _____

- 5.5 a. **Patients who have not started post-surgical hormone therapy:** Patients must have a post-operative serum prostate specific antigen (PSA) less than or equal to 0.2 ng/ml documented after surgery and within 28 days prior to registration.
- b. **Patients who have already started post-surgical hormone therapy:** Patients must have a post-operative serum prostate specific antigen (PSA) \leq 0.2 ng/ml documented after surgery, but prior to the start of hormonal therapy. This may have been more than 28 days prior to registration.
- c. **Patients who started hormone therapy prior to prostatectomy:** Patients must have a post-operative serum prostatic specific antigen (PSA) \leq 0.2 ng/ml documented after surgery but prior to the start of post-surgical hormone therapy. This may have been more than 28 days prior to registration.
- 5.6 The institutional pathology report documenting eligibility for this study must be available for submission as outlined in Section 14.6.
- 5.7 All patients registered on or after June 15, 2006 must be offered the opportunity to consent for specimen banking per Section 15.0.

SWOG Patient No. _____

Patient's Initials (L, F, M) _____

- ____ 5.8 Patients with PSA at clinical diagnosis \geq 20 ng/ml must have a bone scan not suggestive of metastatic disease done within 180 days prior to registration.
- ____ 5.9 Patients with symptoms of distant metastatic disease must have appropriate tests to evaluate for metastatic disease within 56 days prior to registration. Patients with confirmed distant metastatic disease are ineligible.
- ____ 5.10 Patients must have a baseline EKG to rule out underlying cardiac disease within 42 days prior to registration. Patients with a history of cardiac disease, specifically CHF are ineligible unless their disease is well-controlled and they have LVEF \geq 50% by MUGA or 2-d echo within 42 days prior to registration.
- ____ 5.11 Patients known to be HIV positive are not eligible because of the potential to confound the study's endpoint, although patients will not routinely be screened for HIV.
- ____ 5.12 No other prior malignancy is allowed except for the following: adequately treated basal cell or squamous cell skin cancer, adequately treated Stage I or II cancer from which the patient is currently in complete remission, or any other cancer from which the patient has been disease-free for 5 years.
- 5.13 If Day 28, 42, 56, 120 or 180 falls on a weekend or holiday, the limit may be extended to the next working day.

In calculating days of tests and measurements, the day a test or measurement is done is considered Day 0. Therefore, if a test is done on a Monday, the Monday four weeks later would be considered Day 28. This allows for efficient patient scheduling without exceeding the guidelines.

- ____ 5.14 All patients must be informed of the investigational nature of this study and must sign and give written informed consent in accordance with institutional and federal guidelines.
- ____ 5.15 At the time of patient registration, the treating institution's name and ID number must be provided to the Data Operations Center in Seattle in order to ensure that the current (within 365 days) date of institutional review board approval for this study has been entered into the data base.

6.0 STRATIFICATION FACTORS/RANDOMIZATION SCHEME

- 6.1 At the time of registration, patients will be randomly assigned to either Arm 1 or Arm 2 according to a dynamic allocation scheme. The treatment arms will be balanced with respect to the following factors:
- a. Pathologic stage of disease:
 1. organ confined (pT2a - pT2b with either ± surgical margins), but N0,
 2. not organ confined (\geq pT3), but N0,
 3. N1 (any T).
 - b. Gleason's sum: < 7, 7, > 7.
 - c. RT planned: Yes vs. No.

7.1 Good Medical Practice

The following pre-study tests should be obtained within 28 days prior to registration and the following guidelines should be met in accordance with good medical practice. Results of these tests do not determine eligibility and minor deviations would be acceptable if they do not impact on patient safety in the clinical judgement of the treating physician. The Study Coordinator must be contacted if there are significant deviations in the values of these tests.

- a. Patients should have AGC \geq 1,500 cells/mm³, and platelet count \geq 100,000 cells/mm³, SGOT \leq 2.5 X institutional upper limits of normal and serum bilirubin \leq institutional upper limit of normal done within 28 days prior to registration.
- b. Patients must have recovered from major infections and/or surgical procedures and, in the opinion of the investigator, not have significant active concurrent medical illness precluding protocol treatment or survival.

It is recommended that patients have a lymph node dissection in conjunction with the radical prostatectomy within 120 days prior to registration.

7.2 Patients will be randomized to:

Arm 1: Casodex® + Zoladex® for two years.

Arm 2: Chemotherapy (mitoxantrone + prednisone) x 6 cycles plus Casodex® + Zoladex® x 2 years.

7.3 Arm 1 - Hormonal therapy

- a. Zoladex 10.8 mg depot given subcutaneously once every 3 months (13 weeks) for a total of 8 injections given over 2 years, concurrent with Casodex 50 mg orally once daily everyday for two years.
- b. Neo-adjuvant or adjuvant hormonal therapy started prior to registration may be counted as protocol treatment if it included an LHRH agonist (e.g., goserelin acetate, leuprolide acetate, triptorelin) and there was no interruption in treatment. This could be either an LHRH agonist alone or in combination with antiandrogen, but antiandrogen alone will not be counted as pre-registration protocol treatment. Patients must receive a total of 2 years of treatment with LHRH agonist, where the treatment duration of any LHRH agonist received prior to registration may be counted as part of the 2 years of protocol treatment only if that treatment duration was continuous up to the date of registration. It is recommended that patients also complete 2 years of concurrent antiandrogen treatment, but if LHRH agonist was started alone prior to registration the duration of antiandrogen treatment can be shortened to the remaining time of hormonal deprivation after starting the protocol. For patients beginning LHRH agonist prior to registration, every effort should be made to conform to the LHRH agonist administration schedule that is specified in the study calendar, which may mean administering a few doses of single-month depot at the beginning to get on track. All prior hormonal therapy must be documented on the S9921 Local Prostate Carcinoma Prestudy (Form # 23968).

Treatment Schedule

Agent	Dose	Route	Days	ReRx Interval
LHRH Agonist: Goserelin acetate (Zoladex®)	10.8 mg	SC	1	q 3 months (13 weeks) x 8
Anti-androgen: Bicalutamide (Casodex®)	50 mg	Oral (once daily)		1-730 (2 years)

All continuous hormonal treatment counts towards protocol treatment.

7.4 Arm 2 Mitoxantrone and Prednisone + Hormonal Therapy

The administration of Casodex + Zoladex + mitoxantrone + prednisone will commence simultaneously.

- a. Hormonal therapy: Follow same guidelines as Arm 1.
- b. Mitoxantrone 12 mg/m² intravenously every 21 days, plus prednisone 5 mg/dose, BID orally given Days 1-21. A total of 6 courses will be administered. At the end of prednisone treatment (21 days after last mitoxantrone dose), prednisone should be tapered over 2 - 3 weeks at the discretion of the treating physician.

NOTE: Protocol treatment on Arm 2 is not considered complete until patients have completed the 2 years of hormonal therapy. Do not submit an Off Treatment Notice until patient is off **all** protocol treatment.

Agent	Dose	Route	Days	Interval
Mitoxantrone	12 mg/m ²	IV over 30 min	1	q 21 days X 6
Prednisone	5 mg/dose, BID	Oral	1 - 21	continuous q 21 days x 6

7.5 Radiation Therapy:

All RT must be recorded on the S9921 Treatment Form (Form #38859).

Radiation therapy will begin upon recovery from chemotherapy (ideally 3 - 6 weeks and no later than 8 weeks) for patients on Arm 2, and should begin no later than 4 weeks after the initiation of androgen ablation for patients on Arm 1.

Radiation therapy for patients on either arm of the study will be allowed at the physician's discretion following these suggested guidelines:

Doses: The target volume will be the prostate fossa and immediate periprostatic tissue. The minimum and maximum allowable doses will be 6,480 cGy and 7,100 cGy respectively at a dose of 180 - 200 cGy per day. Conedown of the fields at 4,400 - 4,600 cGy is allowed (see portals below).

Radiation Portals: Whole pelvis radiation is not allowed. Initial ports can have more generous margins than those outlined below, but after the initial 4,400 - 4,600 cGy should be coned down to those margins. The goal is to treat the prostate fossa. Treatment of the seminal vesicle (SV) fossa is left to the discretion of the treating physician. For SV negative patients it is probably not necessary. For SV positive patients, it is usually the base of the seminal vesicle that is involved and it may not be desirable to cover the whole SV fossa to the full dose out of concerns for toxicity. If a preoperative CT is available, it can be used in planning, with a margin of 1.5 cm around the prostate and if treated, the SV. For simulation, rectal and urethral or bladder contrast is required.

Four-field technique (recommended) can be planned with 3D conformal technique. IMRT is allowed as long as boundary parameters are met. The NCI's IMRT guidelines can be found on the Advanced Technologies Consortium website (<http://atc.wush.edu> under "News", then "NCI IMRT Letter").

AP/PA ports:

Inferior margin will be at or below the ischial tuberosity (or if urethrogram is used, > 0.5 cm below the narrowing of the urethra).

Lateral margin will be minimum of 1.0 cm lateral to the midpoint of the obturator foramen (usually a field width of 8 to 9 cm).

Superior margin for prostate only or to include the base of the SV is 2 cm above the pubic symphysis. For the entire SV is at the top of the femoral head.

Lateral ports:

Inferior margins as for the AP/PA ports.

Lateral margins - anterior: 1 cm anterior to the junction of the projection of the posterior pubic symphysis over the superior ramus of the pubis or at the tip of the pubic symphysis.

Posterior: 1 cm posterior to a line from the posterior acetabulum and posterior obturator foramen. As much rectum as possible needs to be spared, but at the minimum the anterior 1 cm will be included in the port. This would usually put the block in the mid rectum. A larger portion of the rectum may need to be covered if the rectum subluxed into the prostate fossa. The rectum above the midpoint of the femoral head can be blocked entirely.

Superior: margins for the prostate only and base of the SV would be as for the AP/PA ports. The anterior bladder can be blocked from a line 1 cm anterior to the junction of the projection of the pubic symphysis over the superior ramus of the pubis through the center of the femoral head. Unless the entire SV fossa is to be covered the area posterior to the acetabulum can be blocked.

Beam Energy: Megavoltage equipment with effective photon energies greater than 6 MV is required.

Treatment Distance: Minimum SSD and SAD distance is 80 cm.

Fractionation: 180 - 200 cGy per day five days a week with one set of portals treated each day.

Treatment Planning: Isodose distribution at the mid-transverse plane of the tumor volume and the central axis (if different).

Localization films: If a cone down is done, both fields can be on the same set of films if they are the basis for both treatment.

- a. Patients will be evaluated weekly for toxicity during radiotherapy and all toxicities documented on the S9921 Adverse Event Summary Form (Form #27242).
- b. Post radiation follow-up: Follow-up will be in accordance with the Study Calendar.
- c. Radiotherapy information will be recorded on the S9921 Treatment Form (Form #38859).

7.6 There is a tumor bank for this study for patients with adequate tissue available. In order to have tissue submitted, patients must consent to submission of tissue. Please see Section 15.0 for details of tissue submission.

7.7 Criteria For Removal From Protocol Treatment

- a. Unacceptable toxicity.
 - b. Completion of 2 years of hormonal therapy per protocol.
 - c. The patient may withdraw from the study at any time for any reason.
 - d. Disease progression.
- 7.8 All reasons for discontinuation of treatment must be documented in the Off Treatment Notice (Form #8756).
- 7.9 All patients will be followed 15 years or until death.

8.0 TOXICITIES TO BE MONITORED AND DOSAGE MODIFICATIONS

- 8.1 Patients will be evaluated and graded for toxicity every visit as specified on the Study Calendar for subjective/objective evidence of developing toxicities according to the NCI Common Toxicity Criteria version 2.X (see Section 19.1).
- 8.2 Arm 1 – Hormone therapy
- a. There are no dosage adjustments for hematologic toxicity.
 - b. The most common side effects of anti-androgen therapy are breast pain and gynecomastia. No dose modification is needed except in very severe cases (Grade 3 or higher). In such cases, the anti-androgen will be discontinued permanently and LHRH agonist therapy continued.
 - c. Antiandrogens may be omitted in the case of hepatic toxicity of any severity (at the discretion of the treating physician).
 - d. Hot flashes may develop in patients treated with LHRH agonists. In general, these will not require therapy as resolution is expected following completion of protocol treatment (termination of therapy).
- 8.3 Arm 2 – Mitoxantrone and prednisone + hormone therapy (follow guidelines in Section 8.2 for toxicities attributable to hormone therapy). If mitoxantrone is delayed due to toxicity, prednisone is given on schedule without dose reduction.

- a. Myelosuppression:

See table below for a summary of dose modifications for myelosuppression.

Grade 1, 2 and 3 myelosuppression (leukopenia, neutropenia, thrombocytopenia) and Grade 4 leukopenia or Grade 4 neutropenia except as defined below, with recovery within twenty-one days, does not require dose modification. Patients who do not recover WBC or platelet counts to ≤ CTC Grade 1 toxicity within 21 days should be reduced to dose level -1 for all subsequent courses.

In order to maximize dose intensity, patients with afebrile Grade 4 neutropenia ≥ 7 days or Grade 3 or 4 neutropenia associated with fever (one reading of oral temperature > 38.5°C, or three readings of oral temperature > 38.0°C in a 24-hour period) should be retreated after recovery at the dose level -1.

Grade 4 thrombocytopenia (platelet count < 25,000) at any time necessitates retreatment after recovery at the dose level -1.

G-CSF is not permitted.

Dose Modifications for Myelosuppression.

Dose Level	Mitoxantrone Dose (mg/m ²)
Starting Level	12
Level -1*	9

*This is a permanent dose reduction. Further dose reduction requires removing patient from protocol treatment.

b. Gastrointestinal

Appropriate symptomatic treatment of nausea and/or emesis, diarrhea, mucositis, and/or abdominal pain is permitted.

c. Cardiovascular

The total cumulative dose of mitoxantrone is anticipated to $\leq 72 \text{ mg/m}^2$; based on 6 cycles of 12 mg/m^2 ; EKG changes, arrhythmias, tachycardia, and/or chest pain should be managed based on the specific findings. Patients who have underlying cardiac disease or CHF, will undergo baseline ejection fraction determination echocardiogram or MUGA and this evaluation will be repeated for all patients every two courses. If MUGA decreases to below institutional limits (or $< 15\%$) discontinue protocol treatment.

d. Allergic:

Patients who experience Grade 3 or 4 hypotension, urticaria, or severe rash should be removed from protocol treatment.

e. Hepatic (\geq Grade 2):

Delay mitoxantrone treatment for up to 4 weeks until transient increases in SGOT or hyperbilirubinemia have resolved to Grade 1 or less. If toxicity has not resolved within 4 weeks discontinue protocol treatment.

f. Other:

If toxicities \leq Grade 2, manage symptomatically, if possible and retreat without dose reduction.

If toxicities \geq Grade 3, drug should be withheld (except for alopecia or anemia) until resolution to \leq Grade 1 or baseline if baseline was greater than Grade 1, then reinstated, if medically appropriate, at a dose of 9 mg/m^2 (permanent dose reduction).

8.4 For chemotherapy treatment or dose modification related questions please contact [name] at [name] or [name] at [name]. For urology related questions please contact [name] at [name]. For radiation therapy related questions please contact [name] at [name].

8.5 Unexpected or fatal toxicities (including suspected reactions) must be reported to the Operations Office, to the Study Coordinator, to the IRB and the NCI. The procedure for reporting adverse reactions is outlined in Section 16.0.

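### Read literally, two Arm 2 stopping rules (8.3a footnote and 8.3c) end the shared two-year hormonal therapy as well as the chemotherapy

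*Combined protocol and SAP*

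**What the plan says.** **The stopping rules for Arm 2 (Section 8.3).**
- 8.3a allows one permanent mitoxantrone reduction, from 12 to 9 mg/m². The table footnote adds: "Further dose reduction requires removing patient from protocol treatment".
- 8.3c: "If MUGA decreases to below institutional limits", protocol treatment is to be discontinued.
- 8.3d: patients with Grade 3 or 4 hypotension, urticaria, "or severe rash should be removed from protocol treatment".
- 8.3e, for hepatic toxicity, begins "Delay mitoxantrone treatment for up to 4 weeks" and ends "If toxicity has not resolved within 4 weeks discontinue protocol treatment".

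**The hormonal rules (Section 8.2).** The opening of 8.3 tells sites to "follow guidelines in Section 8.2 for toxicities attributable to hormone therapy". For hormones, 8.2a says "There are no dosage adjustments for hematologic toxicity" and 8.2c says "Antiandrogens may be omitted in the case of hepatic toxicity of any severity". Section 8.2b stops only the anti-androgen for severe breast effects and keeps the LHRH agonist going.

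**What protocol treatment means.** The 7.4 NOTE treats Arm 2 protocol treatment as unfinished until the two hormonal years are done. Section 7.7b ties completion to the same two years, and the title of 14.8 expressly includes hormonal therapy on both arms.

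**What is required.** Section 7.3b makes a total of two years of LHRH agonist mandatory, counting continuous pre-registration use, and 7.4a applies the Arm 1 hormonal guidelines to Arm 2. Section 7.7a allows removal for unacceptable toxicity on either arm.

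**The concern.** Section 11.1 compares combined androgen blockade with the same blockade plus mitoxantrone and prednisone. Hormonal therapy is meant to be the common background. A site that follows the 8.3a footnote or 8.3c to the letter withdraws that background because of a chemotherapy toxicity, and so only on Arm 2. If the physician does not then continue hormones off protocol, Arm 2 has less hormonal exposure for a reason that does not exist on Arm 1. That could reduce an observed benefit of chemotherapy. Section 11.5 has the Statistical Center watch for differential radiotherapy between the arms, but Section 11 provides no such check on hormone duration.

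**Working it through.** **1. Text comparison.** The 8.3a footnote and 8.3c name neither mitoxantrone nor chemotherapy as what stops. Section 8 does separate components when it means to: 8.2b stops one hormonal drug and keeps the other, and 8.3e first delays mitoxantrone and then, in its next sentence, ends protocol treatment. In 8.2d the term must include the LHRH agonist, because hot flashes are expected to resolve once protocol treatment is over. No sentence in 7.4, 7.7, 8.3 or the calendar says that hormones continue after a toxicity stop of mitoxantrone. The literal reading is therefore available, and it contradicts 7.3b with 7.4a.

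**2. Per-patient ceiling.** Inputs: mitoxantrone every 21 days × 6 (7.4b), so Days 1, 22, 43, 64, 85, 106; goserelin every 13 weeks × 8 (7.3a), so Days 1, 92, 183, … 638. The full course is 8 × 91 = 728 days = 104 weeks. Hormones are assumed to start on Day 1.

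| Rule | Possible stop days | Depots given |
|---|---|---|
| 8.3a (first reduction at cycle 2 at the earliest, so second need at cycle 3 or later, on schedule) | 43, 64, 85 / 106 | 1 / 2 |
| 8.3c (every two courses; assumed before cycles 3 and 5) | 43, 85 | 1 |
| 8.3e (dose due at cycles 2–6, plus 28 days) | 50, 71 / 92 / 113, 134 | 1 / second due that day / 2 |

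Share of the course no longer protocol-directed:
- After 1 depot: (728 − 91)/728 = 637/728 = 87.5%.
- After 2 depots: (728 − 182)/728 = 546/728 = 75%.

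These shares fall if pre-registration LHRH agonist counts. As the assumed maximum, take 4 months neoadjuvant (5.4; 122 days) plus 120 days from surgery to registration (5.1), all continuous: 242 days. Then (728 − 242 − 91)/728 = 395/728 = 54.3%, and (728 − 242 − 182)/728 = 304/728 = 41.8%.

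**3. Reach of 8.3c.** The text of 8.3c repeats ejection-fraction testing for all patients. The 9.2 calendar footnote limits it to those who needed a baseline test. If the footnote governs, few patients can meet this trigger.

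**4. Power, as illustration only.** First the plan's figure. With λ = ln 2/median, accrual A = 9.5 and follow-up F = 4 years, deaths per arm = 680 × {1 − [exp(−λF) − exp(−λ(A+F))]/(λA)}. That gives 302.5 (median 10 years) + 249.0 (median 13 years) = 551.4; half is 275.7, against the stated 275. Power = Φ(½√551.4 × ln 1.3 − 1.645) = 0.924, which matches the stated 0.92.

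Now assume that a share q of Arm 2 stops all treatment early, with hazard ratio h against control, and that the arm's hazard ratio is exp[(1 − q) ln(1/1.3) + q ln h]. Deaths are recomputed each time.

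| q | h = 1.0 | h = 1.3 |
|---|---|---|
| 2% | 0.916 | 0.906 |
| 5% | 0.901 | 0.873 |
| 10% | 0.873 | 0.800 |
| 20% | 0.800 | 0.594 |

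The h = 1.0 column can be read as losing the chemotherapy benefit alone, which corrected wording would not prevent. On that reading, only the step to the h = 1.3 column is attributable to lost hormones. The documents supply neither q nor h.

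**The case against.** The best defence is that no site would read the rules this way. Section 7.3b requires two years of LHRH agonist, and the Arm 2 calendar note says treatment runs for two years. The 8.3a footnote sits under a table of mitoxantrone doses. The 7.4 NOTE assumes patients who have finished chemotherapy but are still on hormones. The January 2007 closure memorandum stopped mitoxantrone while recommending that both arms complete their hormones. Section 8.4 names contacts for dose questions. All this is good evidence of intent, and I accept it as such. It shows a conflict within the protocol without resolving it: the memorandum does not amend 8.3, and a contact list does not change a rule.

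The defence is stronger for 8.3d and 8.3e. All four drugs start together on Arm 2, bicalutamide can alter liver function (3.1b), and 3.2c foresees surgical removal of a goserelin depot after severe anaphylaxis. Stopping everything after a severe allergic event, or after hepatic toxicity that persists for four weeks, is a defensible safety rule when the cause is uncertain. A reader might infer that all four rules are equally faulty, but the documents do not support that.

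It is also fair to say that harm is conjectural. The bar on other therapy in 5.4 applies only during protocol treatment. The Off Treatment Notice asks about further treatment, and the Follow-Up Form asks about non-protocol therapy. Hormones could therefore continue after removal.

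**Conclusion.** The point holds for the 8.3a footnote and 8.3c as a fault of wording: they conflict with 7.3b and 7.4a and, if followed literally, end protocol-directed hormones on Arm 2 only. For 8.3e it holds when the event is attributed to mitoxantrone and not to a hormonal drug. Section 8.3d can stand as a safety stop with a narrow exception.

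Two stronger conclusions are tempting. One is that Arm 2 patients actually lost 75% to 87.5% of their hormones. Those figures are per-patient ceilings on protocol direction under a Day 1 start; they do not measure lost exposure, and nothing shows how sites acted. The other is that the primary comparison is biased beyond use or underpowered. The comparison by randomized arm remains valid, and 7.9 follows all patients for 15 years or until death. The number affected and the effect on power are unknown. On the assumptions above, any loss is small if these stops were rare.

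**What to change.** In the 8.3a footnote and 8.3c, write: *discontinue mitoxantrone and prednisone (taper prednisone); continue hormonal therapy to complete 2 years, subject to 8.2 and 7.7*. In 8.3e, use the same wording when the event is attributed to mitoxantrone and not to bicalutamide or goserelin. Leave 8.3d as a safety stop, but let hormones continue if the treating physician attributes the reaction to mitoxantrone. In either section, withhold a suspect hormonal agent, including goserelin.

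These are short text edits that change no design figure. Because mitoxantrone distribution ended in January 2007, they cannot help patients already treated. For them, the only live step is a descriptive table by randomized arm of LHRH-agonist duration and reason for stopping. Sources are the treatment form (#38859), prestudy form (#23968) and Off Treatment Notice, the flow sheets and form versions that these replaced, and the EPP equivalents in Appendix 19.2. The current treatment and prestudy forms date from March 2006, so the table can go only as far as earlier versions captured the dates. Hormones given off protocol can be shown separately as yes/no with a start date from the Follow-Up Form. The cost is one table, plus some work to reconcile older and EPP forms.
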